2.6 Center and Country Effect

Not applicable. This is a single centre study.

2.7 Handling Missing Data

Missing values will not be imputed.

2.8 Medical Coding

Adverse Events will be coded according to MedDRA. MedDRA preferred terms and system organ class will be used for AE summaries. Concomitant medications and medical and ophthalmic histories will not be coded.

2.9 Analysis Populations

2.9.1 Intent-to-Treat Analysis Set

The Intent-to-treat (ITT) Analysis Set will consist of all randomized subjects regardless of whether or not the subject received study drug.

The ITT analysis set will be used for baseline summaries and as secondary analysis set for pharmacodynamics analysis.

2.9.2 *Per-protocol Analysis Set*

The Per-protocol (PP) Analysis Set will consist of all ITT Analysis Set subjects who have no major protocol deviations and who complete the study up to the end of the post-study assessments (i.e. attended the follow-up visit).

Major protocol deviations will be identified by the sponsor and provided to the statistician in order to create the per-protocol analysis set.

The PP analysis set will be used as primary analysis set for pharmacodynamics analysis.

2.9.3 *Safety Analysis Set*

The Safety Analysis Set will consist of all subjects who receive any amount of study drug (including placebo). All safety analyses will be conducted in this population. Safety analysis will be performed according to actual treatment.

2.9.4 *Pharmacokinetic Analysis Set*

All subjects who receive any amount of study drug will be included in the formal analysis of pharmacokinetic parameters providing they have at least one evaluable pharmacokinetic sample.

All pharmacokinetic analyses will be conducted in this population.

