6.1.7 Evaluation of Ocular Discomfort

An evaluation of ocular discomfort will be performed by the Investigator at the times outlined in the Time and Events table (Table 1 and Table 2). A global ocular discomfort score will be determined using a 100 mm VAS on which 0 means no symptoms and 100 means the worst possible discomfort. The following symptoms will be assessed:

Burning
Stinging
Itching
Foreign body sensation
Blurred vision

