9.3.3 Safety Analysis Set

The Safety Analysis Set will consist of all subjects who receive any amount of study drug. All safety analyses will be conducted in this population.

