1.3.2 Secondary Endpoints

- The concentration of PP-001 in plasma at predose, postdose (30 min and 1h \pm 5 minutes after dosing), day 8 and day 19 (30 min \pm 5 minutes after last dosing of the day) will be determined.
- Pharmacodynamic parameters relating to the eye as assessed through:
 - Best corrected visual acuity
 - Visual field
 - Intraocular pressure
 - Slit lamp examination
 - ad slit lamp examination: Conjunctival hyperemia according to the Efron scale (cohort 4 only)
 - Dilated fundoscopy
 - Fundus photography (cohorts 1-3 only)
 - Amsler grid
 - OSDI score (cohort 4 only)
 - Tear film osmolarity (cohort 4 only)
 - Tear film break up time (cohort 4 only)

- Corneal fluorescein staining (cohort 4 only)
- Conjunctival staining using lissamine green (cohort 4 only)

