5. PHARMACOKINETICS / PHARMACODYNAMICS ANALYSIS

Pharmacokinetics:

The PP-001 concentrations in plasma will be listed.

Pharmacodynamics:

The following information will be analyzed descriptively and corresponding details on the subject level will be provided in data listings (Note: Some parameters are just available for either Cohort 1-3 or Cohort 4):

- Best corrected visual acuity
- Visual field
- Intraocular pressure
- Dilated fundoscopy
- Fundus photography
- Amsler grid
- Ocular Surface Disease Index
- Tear film osmolarity
- Slit lamp examination
- Tear film break up time
- Corneal staining with fluorescein

- Conjunctival staining using lissamine green
- Evaluation of ocular discomfort

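### SAP 5 files ocular discomfort, which the protocol places among its safety assessments, under pharmacodynamics, so its designated primary set is per-protocol and not the Safety Analysis Set (minor)

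*SAP*

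**What the plan says.** **Protocol.** Section 6.1.7 is the last item under 6.1, Safety Assessments: "A global ocular discomfort score will be determined using a 100 mm VAS". It names burning, stinging, itching, foreign body sensation and blurred vision as the symptoms assessed. The measure does not appear under 6.3, Pharmacodynamic Procedures, or among the pharmacodynamic endpoints in 2.4. For the Safety Analysis Set, 9.3.3 states: "All safety analyses will be conducted in this population".

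**SAP.** Section 1.3.2 gives the pharmacodynamic endpoints ("Pharmacodynamic parameters relating to the eye as assessed through") without ocular discomfort. Section 5 ends its Pharmacodynamics list with "Evaluation of ocular discomfort". Section 6, Safety Analysis, does not mention it. The rules on analysis sets are:

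- SAP 2.9.1: "The ITT analysis set will be used for baseline summaries and as secondary analysis set for pharmacodynamics analysis".
- SAP 2.9.2: "The PP analysis set will be used as primary analysis set for pharmacodynamics analysis". Membership requires attendance at the follow-up visit and no major deviation, and "Major protocol deviations will be identified by the sponsor and provided to the statistician in order to create the per-protocol analysis set".
- SAP 2.9.3 repeats that safety analyses use the Safety Analysis Set and adds: "Safety analysis will be performed according to actual treatment".

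The planned pharmacodynamic outputs are Table 3.1.1 (ITT), Table 3.2.1 (the same for per-protocol) and Listing 3.2 (ITT, with a column for per-protocol membership). SAP 7 plans no discomfort output on the Safety Analysis Set.

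**The concern.** The primary objective is safety and tolerability, and a symptom scale for eye drops measures tolerability directly. A per-protocol set keeps subjects who finished without a major deviation. It is a poor primary set for such a measure, because leaving the study or deviating from it may itself follow from poor tolerability. If the subjects removed had more discomfort than those kept, the designated primary summary would look more favourable than the experience of everyone dosed. The arms are small, so one subject can move a mean visibly.

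**Working it through.** **1. Where the measure is classified**

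| Place | Role given to ocular discomfort |
|---|---|
| Protocol 6.1.7 | Safety assessment |
| Protocol 6.3 | Not listed as a pharmacodynamic procedure |
| Protocol 2.4, SAP 1.3.2 | Not listed as a pharmacodynamic endpoint |
| Protocol 2.3 and 9.4.1, SAP 1.3.1 | Not named among the safety endpoints or variables |
| SAP 5 | Pharmacodynamics |
| SAP 6.1 to 6.3 | Not listed |

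SAP 5 has 13 pharmacodynamic items. Twelve have a counterpart in SAP 1.3.2, and ocular discomfort is the only one that does not. This looks like a single misplaced item.

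**2. What follows for the analysis set.** Listed in SAP 5, the measure falls under SAP 2.9.2 and its primary set is per-protocol. Treated as a safety measure, it falls under Protocol 9.3.3 and SAP 2.9.3 and its set is the Safety Analysis Set. The two rules give different primary summaries for the same data.

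**3. How much data one missed visit removes.** The discomfort row of Protocol Table 1 has 12 marks: Day 0 before and after dosing, then Days 1, 2, 6, 8, 9, 10, 15, 19, 21 and 28. A Cohort 1-3 subject who misses only Day 28 leaves the per-protocol set and takes the other 11 assessments along (10 without the Day 1 telephone call). Table 2 has 7 marks: Days 0, 1, 2, 7, 11, 13 and 20. Missing only Day 20 removes the other 6. How many of these are scale readings is uncertain, because a footnote to Table 2 ties the row to standardised questions.

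**4. Effect on a mean.** The documents have no figure to reproduce here. Let n be the size of the full set at a visit, k the number outside the per-protocol set, m the mean of those kept, and d the excess of those removed.

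- Full-set mean = [(n − k)m + k(m + d)]/n = m + (k/n)d
- Per-protocol mean = m
- Difference = (k/n)d

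The values of n are planned sizes: 6 active and 2 placebo in each of Cohorts 1 to 3, giving 3 × 6 = 18 active and 3 × 2 = 6 placebo pooled, and 14 active and 7 placebo in Cohort 4. The documents give neither k nor d. I assume k = 1 and d from 10 to 50 mm.

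| Column | n | Difference, d = 10 mm | Difference, d = 50 mm |
|---|---|---|---|
| One active cohort of 1-3, or pooled placebo 1-3 | 6 | 10/6 = 1.7 | 50/6 = 8.3 |
| Cohort 4 placebo | 7 | 10/7 = 1.4 | 50/7 = 7.1 |
| Cohort 4 active | 14 | 10/14 = 0.7 | 50/14 = 3.6 |
| Pooled active 1-3 | 18 | 10/18 = 0.6 | 50/18 = 2.8 |

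SAP 2.11 reports that Cohort 3 stopped early, without its enrolment. If it contributed nobody, the pooled active n is 12 and the difference is 10/12 = 0.8 to 50/12 = 4.2 mm. If d is negative the shift has the same size in the other direction, and if k = 0 it is zero.

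**5. Which tables this compares.** The difference in step 4 is between a full-set table and the per-protocol table. A full-set version is already planned as Table 3.1.1 on ITT. The Safety Analysis Set differs from ITT only if a randomised subject is never dosed or receives the wrong treatment. If all are dosed as assigned, a Safety-set table would equal Table 3.1.1. The correction therefore mainly changes which table is designated primary.

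**The case against.** The best defence is that the designation has little practical force. The pharmacodynamic output is descriptive, the only planned tests are in the adverse event summary (SAP 2.5), and no stated decision rule uses the discomfort score. All randomised subjects appear in Table 3.1.1 and Listing 3.2. New or worsened symptoms are to be reported as adverse events (Protocol 7), and those tables use the Safety Analysis Set. Subjects withdrawn from treatment are to be kept for follow-up where possible (Protocol 6.8). If they attend and have no major deviation, they stay in the per-protocol set. All of this stands and keeps the point minor.

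A second defence is that a section heading does not settle the analysis role. Medical history is also under Protocol 6.1, yet SAP 4 treats it as baseline. That is fair: the safety status of discomfort rests on placement and on what it measures, not on a named endpoint. But its filing under pharmacodynamics has less support, since neither pharmacodynamic endpoint list contains it.

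A reader might be tempted by four stronger readings, which the documents do not support:

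- *That the SAP silently changed a planned protocol analysis.* Protocol 9.6 plans summaries of adverse events, vital signs and laboratory values and none of discomfort, so SAP 2.11 omits no change of a planned analysis.
- *That the order of Tables 3.1.1 and 3.2.1 contradicts the per-protocol designation.* Order does not mark primacy in this SAP. Section 2.9.1 assigns baseline summaries to ITT, yet SAP 7.1 shows them first on the Safety Analysis Set.
- *That the early stop removed Cohort 3 from the per-protocol set.* The SAP says neither whether its subjects attended follow-up nor whether the stop counts as a major deviation.
- *That every code break removes a subject from the set.* Protocol 5.5 excludes such a subject from the study, but does not say that this is a major deviation or that follow-up is missed.

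**Conclusion.** The inconsistency is real and minor. As written, the SAP makes a set of completers without major deviations primary for a measure that the protocol places among its safety assessments, contrary to the rule in both documents that safety analyses use the Safety Analysis Set.

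The possible distortion is confined to the designated primary summary. At planned sizes it is 0.6 to 8.3 mm for one removed subject, and this rests wholly on the assumed k and d. A reader might infer that discomfort data are lost, that a named primary endpoint was moved, or that bias has occurred. None of these follows: the ITT outputs retain the data, Protocol 2.3 does not name the measure, and the documents do not say how many subjects leave the per-protocol set or how they scored.

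**What to change.** Before unblinding:

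1. Move the ocular discomfort item from SAP 5 to SAP 6.
2. Make the Safety Analysis Set, by actual treatment, its primary summary: add one table by time point to SAP 7.1, using all available visits.
3. Keep any per-protocol summary of it as supportive only.
4. Note the classification in SAP 2.11, so that a reader can see how it relates to Protocol 6.1.7.

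The cost is one table and a few lines of text. No new data are needed, and the ITT and per-protocol tables for the other pharmacodynamic measures stay as planned.

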2.10 Subject Data Listings

Listings will be sorted by treatment group / cohort, subject ID, and/or parameter and/or visit (in this order), where applicable. Treatment group / cohort will be shown in all listings.

2.11 Changes in the Conduct of the Study or Planned Analysis

In CSP Version 4.0 (March 26, 2021), which is the latest protocol version at the time when writing this SAP, concomitant medication is mentioned erroneously as primary endpoint. This is not included as a primary endpoint in the SAP, since it is not considered a relevant safety endpoint.

The recruitment of the first healthy subject in Cohort 1-3 was in November 2018. In June 2019, the study was placed on-hold while Cohort 3 was in progress, and Cohort 3 was stopped prematurely. The study was re-started with addition of a 4th Cohort which recruits patients with ocular surface inflammation starting in May 2021.

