1. OVERVIEW

1.1 Study Objectives

1.1.1 Primary Objective

The primary objective is to assess the safety and tolerability of 1 day (single dose) and 12 days (48 doses) dosing with ascending doses (0.05% [0.5 mg/mL], 0.15% [1.5 mg/mL] and 0.3% [3.0 mg/mL]) of PP-001 eye drops compared to placebo eye drops in healthy subjects (cohorts 1-3). In addition, safety and tolerability will be tested in a group of 21 patients with ocular surface inflammation (cohort 4).

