2.4 Descriptive Analyses and Columns in Summary Tables

Descriptive analyses of continuous variables (summary statistics) will be described with the number of non-missing observations, arithmetic mean, standard deviation (\pm SD), median, quartiles (Q1 and Q3) and range (minimum and maximum).

Categorical variables (frequency statistics) will be described with the number of non-missing observations and percentages (%). Percentages will be calculated within each stratum on the total number of non-missing observations, if not stated otherwise.

In general, tables will present the following columns:

- Cohort 1 PP-001, 0.05% [0.5 mg/mL], 4 drops per day, healthy subjects
- Cohort 2 PP-001, 0.15% [1.5 mg/mL], 4 drops per day, healthy subjects
- Cohort 3 PP-001, 0.3% [3.0 mg/mL], 4 drops per day, healthy subjects
- Cohort 1-3 PP-001 pooled
- Cohort 4 PP-001, 0.15% [1.5 mg/mL], 2 drops per day, patients with diagnosed ocular surface inflammation
- Placebo subjects from all cohort 1-3
- Placebo subjects from cohort 4
- All subjects (only for overall study information and baseline tables)

The disposition table may also include a column for screening failures. For tables by time point the columns for Cohort 1-3 and Cohort 4 might be shown in a separate table, since Cohort 1-3 have a different visit schedule than Cohort 4.

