6. SAFETY ANALYSIS

6.1 Adverse Events

The following information will be analyzed descriptively and corresponding details on the subject level will be provided in data listings:

- Adverse Event (AE)
- AEs leading to premature discontinuation from the study drug
- Serious AEs
- AEs by severity
- AEs by causality
- AEs by SOC and PT

Definitions:

- In tables showing subjects with AEs by maximum severity, subjects will be counted only in the highest grading category, but events will be counted in each reported grading category.
- In tables showing AEs by maximum causality, subjects will be counted only in the strongest relationship category, but events will be counted in each category.

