7.1 List of Tables

No.	Legend	Comment
Overall study information		
1.1.1	Subject overview (all subjects)	
1.1.2	Protocol deviations (safety analysis set)	
1.1.3	Attended visits with dates (safety analysis set)	
1.1.4	Study completion (safety analysis set)	
1.1.5	Study drug administration (safety analysis set)	
1.2.2 -	Repeat tables for ITT analysis set, if not the same as safety analysis set.	
1.2.5		
Baseline evaluation		
2.1.1	Summary table of demographic information (safety analysis set)	
2.1.2	Summary table for medical and ophthalmic histories and prior and concomitant medication (safety analysis set)	
2.1.3	Non-pharmacologic treatments and procedures (safety analysis set)	
2.2.1 -	Repeat tables for ITT analysis set, if not the same as safety analysis set.	
2.2.3		
Pharmacodynamics Analysis		
3.1.1	Pharmacodynamics by time point (ITT analysis set)	
3.2.1	Repeat table for PP analysis set.	
Safety Analysis		
4.1	Summary table for adverse events (safety analysis set)	Including tests described in section 2.5.
4.2	Adverse events by SOC and PT (safety analysis set)	
4.3	Adverse events by severity (safety analysis set)	
4.4	Adverse events by maximum severity (safety analysis set)	"By maximum severity" is explained in section 6.1.
4.5	Adverse events by causality (safety analysis set)	
4.6	Adverse events by maximum causality (safety analysis set)	"By maximum causality" is explained in section 6.1.
4.7	Laboratory results by time point (safety analysis set)	

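### For Cohorts 1-3 the SAP tabulates adverse events by cohort and treatment only, so neither the single dose nor the 48-dose course named in the primary objective gets its own AE incidence

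*SAP*

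**What the plan says.** - **Objective.** For Cohorts 1-3, SAP 1.1.1 (as Protocol 2.1) sets out to assess "safety and tolerability of 1 day (single dose) and 12 days (48 doses) dosing with ascending doses". SAP 1.2 delivers these two exposures in sequence to the same subjects, under the same allocation. They are separated by at least 7 days and by a decision whether to continue the cohort into Part II.
- **Columns.** SAP 2.4 defines columns by cohort and treatment, for example "Cohort 3 PP-001, 0.3% [3.0 mg/mL], 4 drops per day, healthy subjects". There is also a pooled PP-001 column and a pooled placebo column for Cohorts 1-3. No column or sub-row refers to a Part.
- **AE outputs.** SAP 6.1 and Tables 4.1 to 4.6 in SAP 7.1 cover an overall summary, "AEs by SOC and PT", severity and causality. None is by Part, period or time point. Protocol 9.6 has no such split either.
- **Denominator.** Under SAP 2.9.3 a subject enters the safety set after any amount of study drug. One Part I drop is enough.
- **Conduct.** SAP 2.11 records that "the study was placed on-hold while Cohort 3 was in progress, and Cohort 3 was stopped prematurely". It does not give the reason, the Part reached or the number dosed, and it changes no table.
- **Other outputs.** Pharmacodynamic measures, among them "Evaluation of ocular discomfort" (SAP 5), are tabulated by time point, as are laboratory results. Vital signs and physical examination appear only as listings (SAP 6.3), although Protocol 9.6 foresees vital signs summarised at each visit.

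**The concern.** Adverse events head the list of primary endpoint items in SAP 1.3.1. The design treats the single drop and the 12-day course as separate safety questions, with a go/no-go step between them. The planned tables merge them into one percentage per column. A reader of the study report could not say what proportion of subjects had an AE after one dose, or during the course, without rebuilding it from listings.

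The early stop of Cohort 3 adds a second problem. If some of its subjects had only the Part I drop, they sit in the denominator of the highest-concentration column as if they had taken the full course. Part II-onset AEs in that column would then look rarer beside the two lower concentrations than they were among subjects actually exposed. The same denominators feed the pooled Cohorts 1-3 column and the exploratory Fisher tests of SAP 2.5.

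**Working it through.** **1. The plan's own dose count.** Part II is 4 doses x 12 days = 48, which agrees with SAP 1.1.1. With the Part I dose the planned total is 49, so Part I is 1/49 = 2% of planned doses. Each AE percentage for Cohorts 1-3 covers both Parts over one denominator.

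**2. Which outputs can separate the two exposures?**

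| Item | SAP output | Separates Part I from Part II? |
|---|---|---|
| AEs and SAEs (primary) | Tables 4.1-4.6, no time dimension | No |
| Laboratory tests (primary) | Table 4.7 by time point | No: in Protocol Table 1 routine tests for Cohorts 1-3 fall only at Screening and Day 21 |
| Vital signs (primary) | Listing 4.4 only | Not tabulated |
| Physical examination (primary) | Listing 4.5 only | Not tabulated |
| Pharmacodynamics, including ocular discomfort (secondary) | Tables 3.1.1 and 3.2.1 by time point | Yes: visits fall in both Parts |

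No tabulated primary endpoint item reports the two exposures apart.

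**3. Size of the denominator effect.** Let n be the PP-001 subjects dosed in Cohort 3, m those who entered Part II, and k (at least 1) those with a Part II-onset AE.

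- Share as tabulated: k/n. Share among those exposed: k/m.
- Ratio: (k/n)/(k/m) = m/n, for m of 1 or more. No event risk is assumed.
- At m = 0 no Part II AE can occur, so the ratio is 0/0 and the Part II share is not estimable.

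The documents give neither m nor n. The table below assumes the planned n = 6. The pooled column further assumes that all 6 + 6 = 12 PP-001 subjects of Cohorts 1 and 2 entered Part II, so its ratio is (12 + m)/18. The last column is the exact one-sided 95% upper limit when no Part II AE is seen, 1 - 0.05^(1/m).

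| m | Cohort 3: m/6 | Pooled: (12 + m)/18 | Upper limit at 0 of m |
|---|---|---|---|
| 6 | 1.00 | 1.00 | 39.3% |
| 5 | 0.83 | 0.94 | 45.1% |
| 4 | 0.67 | 0.89 | 52.7% |
| 3 | 0.50 | 0.83 | 63.2% |
| 2 | 0.33 | 0.78 | 77.6% |
| 1 | 0.17 | 0.72 | 95.0% |
| 0 | not estimable | 0.67 | not estimable |

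For example, a table implying 0 of 6 suggests that a Part II risk above 39.3% is excluded. If only three subjects entered Part II, the data exclude only a risk above 63.2%.

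**4. A Part I window that is equal for everyone.** On the fastest permitted schedule, 1 + 1 + 2 + 4 = 8 subjects are dosed on calendar days 0, 1, 2 and 3 (consecutive days assumed). Part II starts at least 7 days after the last of them, on calendar day 3 + 7 = 10. On each subject's own clock that is Day 10, 9, 8 and 7 for the four dosing days, and the footnote to Protocol Table 1 raises the last to Day 8. A window ending at the first Part II dose would therefore differ in length within a cohort. Day 0 to the end of Day 7 precedes Part II for every subject and contains the Day 6(+1) visit.

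**The case against.** - **The plan is flexible.** SAP 2.4 says what tables show in general, SAP 7 lets tables be split further, and Protocol 9 allows additional analyses. AE onset and dosing dates are listed, so the split can be made by inspection. This is true, but it permits the analysis without committing to it, and a listing has no denominator.
- **The m/n figures are an identity, not evidence.** This stands. They span the whole range, and n itself is insecure. It may be below 6 because the cohort stopped while in progress, or above 6 because Protocol 6.8 replaces subjects withdrawn before Day 21 for reasons other than AEs. Since Part II is opened for a cohort as a whole, m = 0 or m close to n may be likelier than the middle values.
- **The split does not cover every case.** This also stands. If dosing stopped during Part II, then m = n and a subject with a few of the 48 doses still counts in full. Only doses received and completion numbers show that.
- **The two incidences will not be directly comparable.** Part I would be 8 days (Day 0-7) and Part II nominally 21 (Day 8-28), in the same subjects and in fixed order, with sparse cells. This calls for a footnote; it is no reason to merge the Parts.

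A reader might infer that the Cohort 3 column understates AE incidence, or that the early stop conceals a safety signal. The documents support neither. They give no reason for the stop and no exposure numbers. If AEs came early or prompted the stop, overall incidence in Cohort 3 need not be low at all.

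**Conclusion.** The omission is certain: followed as written, the plan gives no AE incidence for either exposure in its primary objective for Cohorts 1-3, and no other primary endpoint table makes up for it. That holds whatever happened in Cohort 3.

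The dilution in Cohort 3 is conditional. It is m/n for Part II-onset AEs, nil if every dosed subject entered Part II, and not estimable if none did. The tabulated values rest on the assumed n = 6.

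A reader might go further and conclude that dose escalation or the statistical inference is compromised. It is not. The DSMB decides on escalation during the study (Protocol 3), the SAP foresees one final analysis after database closure (SAP 2.1), and SAP 2.5 labels its p-values exploratory. This is a worthwhile, inexpensive improvement in reporting, not a flaw that invalidates the plan.

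**What to change.** In SAP 6.1 and 7.1, for Cohorts 1-3:

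1. Add descriptive versions of Tables 4.1 and 4.2 by Part of onset, with subjects dosed in that Part as denominator.
2. Define Part I as first dose to the end of Day 7, and Part II as first Part II dose to last follow-up. Show separately any later AE that starts before Part II, or that occurs in a subject who never enters it.
3. State a rule for an AE on the first Part II day with no onset time, for example assignment to Part II. SAP 2.7 imputes nothing, and Protocol 7 records onset time only if available.
4. In Table 1.1.5 and the column headers, show by cohort the numbers entering and completing each Part and the doses received.
5. Footnote that the two windows differ in length, that Part II follows Part I in the same subjects, and that Cohort 3 was stopped early.
6. Keep the overall AE tables and the Fisher tests as planned.

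The cost is SAP wording, one derived flag and one rule for missing times. The dates needed are already collected (Protocol 5.6 and 7). The downside is a few more tables with small counts: about 6 active and 2 placebo subjects per cohort as planned, possibly more with replacements.
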